#### Statistical Considerations

With a sample size of 25 subjects in each treatment arm, assuming 50%, 75%, or 90% of subjects complete 12 cycles of treatment, the expected half-widths of the 95% confidence interval (CI) for estimating the proportion of subjects completing 12 cycles of treatment are provided below.

	95% Cd	onfidence Interval Half-w	idth (%)
Sample Size	50%	75%	90%
25	20.5	18.1	13.5

The full analysis set will be the same as the safety analysis set, which will include all enrolled subjects who received at least 1 dose of any study treatment (ie, carfilzomib, lenalidomide, pomalidomide, or dexamethasone). Unless otherwise specified, following analyses will be based on the safety analysis set.

Protocol Number: 20170596

**Date**: 20 May 2019 Page 16 of 132

For primary endpoints, the proportion of subjects completing 12 cycles of carfilzomib based regimens will be calculated. The proportion of actual cumulative dose received to the full intended cumulative dose in cycles 1-12 will be summarized descriptively. The full intended cumulative dose is defined as all therapy specified per

Sections 7.1.1.2 and 7.1.2 without consideration for dose modification or skipped doses.

Relative dose intensity in cycles 1-12 will be summarized descriptively. Dose modifications including dose reduction, dose withheld, and dose delay in cycles 1-12 will be summarized along with reasons including adverse events and non-adverse events.

Treatment-emergent adverse events and serious adverse events in cycles 1-12 will be summarized descriptively following the methods specified in Section 10.3.2.3. The proportions of treatment discontinuations due to all adverse events, reasons for treatment discontinuation due to all adverse events, and dose reductions due to all adverse events will be summarized descriptively.

All EORTC QLQ-C30 and EORTC QLQ-MY20 subscale scores up to cycle 12 or disease progression will be summarized descriptively by cycle based on the safety analysis set. The rate of PFS at 1 year will be estimated using the Kaplan-Meier method and with CI estimated using the method by Kalbfleisch and Prentice, 1980 with log-log transformation. The response rate and 1-year PFS rate will be summarized descriptively by line of prior therapy 1 vs  $\geq$  2.

For a full description of statistical analysis methods, please refer to Section 10.

Sponsor Name: Amgen Inc.

[figure not shown]
Protocol Number: 20170596

**Date:** 20 May 2019 Page 17 of 132

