**Date:** 20 May 2019 **Page 21 of 132** 

Table 2-1. Schedule of Activities

	Screening a b				Tre	eatr	nen	t P	erio	d				Safety	
	(up to			Су	cle	1-2				C	ycl	e 3-	12	FU c (30	
PROCEDURE	21 days before Day 1)	Day 1	2	8	9	15	16	22	23	1	8	15	21	[+3] days post last dose)	Notes
Bone Lesion Assessment b	х														Screening and will be repeated if worsening clinical symptoms suggest PD, or as clinically indicated. (see Section 12.8 for IMWG criteria)
Plasmacytoma evaluation b	х														See Section 9.2.2.3. Only required at screening in subjects if clinically suspected and to confirm response (if performed at screening, see Section 12.8 for IMWG criteria)
Bone marrow aspirate with FISH b	Х														Bone marrow aspirate is required at screening and to confirm a response of CR (see Section 12.8 for IMWG criteria). FISH is only required at screening.
CLINICAL OUTCOME ASSESSM	MENTS														
EORTC QLQ-C30		Х								Х				X	During treatment period, these
EORTC QLQ-MY20		Х								Х				Х	questionnaires must be completed on day 1 of each cycle prior to dosing.
Amgen Satisfaction and Convenience Questionnaire		x								x				Х	During treatment period, these questionnaires must be completed on day 1 of each cycle prior to dosing, starting with C2D1. Items 8-11 to be collected only once at end of treatment or at completion of the trial.

Page 4 of 7

**Protocol Number:** 20170596

**Date:** 20 May 2019 Page 22 of 132

Table 2-1. Schedule of Activities

	Screening a b				Tre	eatr	nen	t Pe	erio	d				Safety	
	(up to			Су	cle	1-2				С	ycl	e 3-′	12	FU c (30	
PROCEDURE	21 days before Day 1)	Day 1	2	8	9	15	16	22	23	1	8	15	21	[+3] days post last dose)	
STUDY TREATMENT															
Kd ARM															
Carfilzomib administration h		X	×	X	X	X	×			x	x	x			Cycle 1: 20 mg/m² on days 1 and 2; 56 mg/m² on days 8, 9, 15, and 16 Cycle 2: 56 mg/m² Cycles 3-12: 70 mg/m² For subjects with baseline hepatic function abnormalities (bilirubin or AST > ULN), see Section 7.1.1.2.1 for modification of the initial dose. For cycle 3, for subjects who were previously dose reduced, see Section 7.1.1.2 for starting dose.
Dexamethasone administration h		x	х	X	X	X	X	Xi	Xi	х	х	х			Cycles 1-2: 20 mg Cycles 3-12: 40 mg For subjects ≥ 75 years of age, see Section 7.4.1.2 for dose modification.

**Protocol Number:** 20170596

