# 7.1.1.2 Dosage, Administration, and Schedule

For all treatment arms, carfilzomib will be administered at 20 mg/m² on days 1 and 2 of the first cycle (see Table 7-1). For subjects in the Kd arm, carfilzomib will be administered at 56 mg/m² on days 8, 9, 15, and 16 of the first cycle, and then on days 1, 2, 8, 9, 15, and 16 in cycle 2. Starting with cycle 3 through cycle 12, carfilzomib will be administered at 70 mg/m² on days 1, 8, and 15 of each 28-day cycle. For subjects in the KRd and KPd arms, carfilzomib will be administered at 27 mg/m² on days 8, 9, 15, and 16 of the first cycle, and then on days 1, 2, 8, 9, 15, and 16 in cycle 2. Starting with cycle 3 through cycle 12, carfilzomib will be administered at 56 mg/m² on days 1, 8, and 15 of each 28-day cycle.

Protocol Number: 20170596

**Date:** 20 May 2019 Page 50 of 132

At the time of implementation of protocol amendment 3, subjects previously enrolled may have completed more than 2 but less than 6 cycles of twice weekly carfilzomib dosing on the Kd arm as per protocol amendment 2. These subjects should complete the dosing regimen as per protocol amendment 2, (ie, 6 cycles of twice weekly dosing for carfilzomib [Kd 56 mg/m²] transitioning to once weekly dosing for carfilzomib [Kd 70 mg/m²], starting with cycle 7). For these subjects, the schedule of activities outlined per Table 2-1 for cycles 1 and 2 will continue for cycles 1 through 6. At the start of cycle 7, these subjects will then follow the schedule of activities as outlined per Table 2-1 cycles 3 through 12. In addition, the starting nominal dose of carfilzomib on day 1 cycle 7 (which is the initiation of the once weekly carfilzomib dosing for these subjects) should be reduced by the same number of dose levels and same percentage dose reduction as it was reduced to during cycle 6 (which is the twice weekly carfilzomib dosing). Dexamethasone will be administered at a dose of 20 mg once daily on days 1, 2, 8, 9, 15, 16, 22, and 23 cycles 1 through 6 and at a dose of 40 mg once daily on days 1, 8, 15 for the Kd arm for cycles 7 through 12 for these subjects.

All doses should be administered on the scheduled day  $\pm$  2 days, and the day 8 and 15 doses should have at least a 5-day treatment-free interval. The starting dose should be modified for chronic mild hepatic insufficiency per Section 7.1.1.2.1.

Table 7-1. Carfilzomib Dosage

Cycle 1	Cycle 2	Cycles 3-12		
Kd Arm				

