D1, 2: 20 mg/m  D8, 9, 15, 16: 56 mg/m 	D 1, 2, 8, 9, 15, 16: 56 mg/m 	D1, 8, 15: 70 mg/m 		
KRd Arm	KRd Arm			
D1, 2: 20 mg/m  D8, 9, 15, 16: 27 mg/m 	D 1, 2, 8, 9, 15, 16: 27 mg/m 	D1, 8, 15: 56 mg/m 		
KPd Arm				
D1, 2: 20 mg/m  D8, 9, 15, 16: 27 mg/m 	D 1, 2, 8, 9, 15, 16: 27 mg/m 	D1, 8, 15: 56 mg/m 		

D = day

Subjects receiving carfilzomib at doses less than the protocol planned dose (56 mg/m^2 or 27 mg/m^2 based on treatment arm) during cycle 2 may have been reduced by 1 or more dose levels and/or by 25% for hepatic function abnormalities. Subjects should have the starting nominal dose of carfilzomib (70 mg/m^2 or 56 mg/m^2 based on treatment arm) on day 1 cycle 3 reduced by the same number of dose levels and the same

Protocol Number: 20170596

**Date**: 20 May 2019 Page 51 of 132

percentage dose reduction as they were reduced during cycle 2, see Table 7-2 for dose level reductions.

Carfilzomib is to be administered as an IV infusion over 30 (± 5) minutes. Subjects should receive 250 mL of normal saline or equivalent IV fluid prior to and after each dose during cycle 1. After cycle 1, at the discretion of treating physician, subjects may receive up to but no more than 250 mL of normal saline or equivalent fluid prior to each dose of carfilzomib. For subjects at risk of TLS, see Section 7.1.4.3.

Mechanical infusion pumps are recommended, but gravity-dependent infusions are permitted if the 30-minute infusion duration can be reliably maintained. Carfilzomib infusion must occur at a facility capable of managing hypersensitivity reactions.

Each subject's first dose will be calculated based upon baseline BSA per the Mosteller formula. In subjects with BSA of greater than  $2.2 \text{ m}^2$ , the dose should be capped based on a BSA of  $2.2 \text{ m}^2$ . The dose for each subject should not be revised unless the subject experiences a change in body weight of  $\geq 20\%$  compared to baseline or last calculation of BSA, in which case the BSA and dose should be recalculated. The dose can also be modified in response to toxicity following the dose modification guideline tables (see Section 7.4).

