# 7.1.2 Non-investigational Products

# 7.1.2.1 Dexamethasone: Dosage, Administration, and Schedule

For all treatment arms, dexamethasone will be taken orally or by IV infusion at a dose of 20 mg once-daily on days 1, 2, 8, 9, 15, 16, 22, and 23 of Kd cycles 1-2, and at a dose 40 mg once-daily on days 1, 8, 15 of Kd cycles 3-12. All doses should be administered on the scheduled days  $\pm$  2 days but prior to carfilzomib infusion except for days 22 and 23 of cycles 1-2.

Dexamethasone will be administered at least 30 minutes (but no more than 4 hours) prior to carfilzomib. Subjects receiving dexamethasone IV on days 1, 2, 8, 9, 15, and 16, may receive the day 22 and day 23 dose orally.

For subjects  $\geq$  75 years of age, see Section 7.4.1.2 for dose modification.

The dose, date, time, and reason for dose change are to be recorded on each subject's CRF.

Dexamethasone will not be provided or reimbursed by Amgen. The investigator will be responsible for obtaining supplies of dexamethasone.

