#### 7.4 Dose Modification

# 7.4.1 Dosage Adjustments, Delays, Rules for Withholding or Restarting, Permanent Discontinuation

# 7.4.1.1 Amgen Investigational Product: Carfilzomib

The reason for dose change of carfilzomib is to be recorded on each subject's CRF.

Carfilzomib may be discontinued, temporarily delayed, or dosage temporarily reduced, in the event of a treatment-related toxicity that, in the opinion of the investigator, warrants the discontinuation, temporary delay or dose reduction. Carfilzomib dose must be modified based on specified toxicities, as indicated in Table 7-3 and Table 7-4. The subject will be considered on protocol treatment while receiving carfilzomib. Carfilzomib (both twice-weekly and once-weekly regimen) must be discontinued permanently if a delay of more than 6 weeks is required due to unresolved toxicity.

If day 1 of a cycle is delayed, day 1 of subsequent cycles should be adjusted accordingly to maintain the 28-day cycle duration. However, if a within-cycle dose is delayed, then the dates of the subsequent within-cycle doses should not be adjusted.

Protocol Number: 20170596

**Date**: 20 May 2019 Page 58 of 132

If carfilzomib administration does not commence within the allowable window of the scheduled administration date, then the dose will be considered a missed dose. Administration may resume at the next planned dosing date. A missed dose will not be made up.

If either carfilzomib or dexamethasone are held for the remainder of the previous cycle or the new cycle is delayed due to residual toxicity on the planned day 1 of the next cycle, then the new cycle will be started at 1 dose decrement for the drug(s) causing the delay.

For conditions that do not require carfilzomib dose reduction, refer to Section 7.4.1.3.

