# 7.4.1.2 Non-Amgen/Amgen Non-investigational Product: Dexamethasone

The reason for dose change of dexamethasone is to be recorded on each subject's CRF.

For conditions that do not require dexamethasone dose reduction, refer to Section 7.4.1.1.3.

For subjects  $\geq$  75 years of age, the starting dose of dexamethasone should be 20 mg weekly, 10 mg administered on days 1, 2, 8, 9, 15, 16, 22, and 23 during cycles 1-2, and 20 mg administered on the days 1, 8, 15 during cycles 3-12.

<sup>a For a rapid fall from baseline in estimated GFR or an absolute fall of ≥ 60 mL/min/1.73 m², contact the medical monitor.

<sup>b In the event of a possible drug-related nonhematologic toxicity, the investigator should, to the best of his/her ability, assess its relationship to carfilzomib (K), dexamethasone (d), or the combination of Kd to the extent possible. If both carfilzomib and dexamethasone are considered likely to be involved, then recommended actions for both should be instituted.

Protocol Number: 20170596

**Date:** 20 May 2019 Page 63 of 132

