**Date:** 20 May 2019 **Page 84 of 132** 

#### 10.3.2.3 Safety Analyses

#### 10.3.2.3.1 Analyses of Primary Safety Endpoint(s)

Endpoint	Statistical Analysis Methods
Primary	Unless otherwise specified, following analyses will be based on the safety analysis set. The analyses will be carried out for subjects on the Kd, KRd, and KPd regimens, respectively.
	The proportion of subjects completing 12 cycles of Kd, KRd, and KPd treatment will be calculated based on the safety analysis set.
	The proportion of actual cumulative dose received to the full intended cumulative dose in cycles 1-12 will be summarized descriptively. The full intended cumulative dose is defined as all therapy specified per Sections 7.1.1.2 and 7.1.2 without consideration for dose modification or skipped doses. Relative dose intensity in cycles 1-12 will be summarized descriptively. Dose modifications including dose reduction, dose withheld, and dose delay in cycles 1-12 will be summarized along with reasons including adverse events and non-adverse events. Treatment-emergent adverse events and serious adverse events in cycles 1-12 will be summarized descriptively following the methods specified in Section 10.3.2.3.
Secondary	Not applicable
Exploratory	Not applicable

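### The intended-dose rule and the SAP dose table carry only the 20/40 mg dexamethasone schedule, so a fully compliant subject aged 75 or older scores 50% or 100% for dexamethasone depending on which of two conflicting readings is taken

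*Protocol*

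**What the plan says.** **The rule.** The share of the intended cumulative dose actually received in cycles 1-12 is a primary endpoint, and so are dose modifications (Protocol 4.1). Protocol 10.3.2.3.1 defines the denominator: "The full intended cumulative dose is defined as all therapy specified per Sections 7.1.1.2 and 7.1.2 without consideration for dose modification or skipped doses". The synopsis points to the same place: "Sections 7.1.1.2 and 7.1.2 without consideration for dose modification or skipped doses".

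**Dexamethasone.** Section 7.1.2.1 gives 20 mg on eight days per cycle in cycles 1-2 and 40 mg on three days per cycle in cycles 3-12, for all arms. For subjects aged 75 or older it only says "see Section 7.4.1.2 for dose modification". Table 2-1 does the same: "For subjects ≥ 75 years of age, see Section 7.4.1.2 for dose modification". The lower schedule itself (10 mg, then 20 mg, on the same days) stands only in Section 7.4.1.2, under the heading "7.4 Dose Modification". There it is worded differently: "the starting dose of dexamethasone should be 20 mg weekly". Table 7-5 lists two nominal dexamethasone doses, 40 mg and 20 mg, with weekly reduced doses beside them.

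**SAP.** Section 5 takes planned dose as the sum of the doses the protocol specifies for the subject, then supplies one table: 20 mg and 40 mg dexamethasone, with no row for age. It calls any administration below the specified dose a dose reduction. The SAP is dated 08 June 2018 and serves the Kd-only protocol of 06 March 2018.

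**Carfilzomib with mild hepatic insufficiency.** The lower start is in 7.1.1.2.1, inside a cited section. Yet 7.1.1.2 says "The starting dose should be modified for chronic mild hepatic insufficiency per Section 7.1.1.2.1", and its paragraph beginning "Subjects receiving carfilzomib at doses less than the protocol planned dose" names a 25% hepatic reduction as one way of being below plan.

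**The concern.** The age-75 schedule lies outside the two sections the rule names, and it carries the label that the rule tells the analyst to disregard. Someone programming the endpoint from the text would put 20/40 mg in the denominator for everyone. A subject who did exactly what the protocol asked would then be recorded as having received half the intended dexamethasone, and also as having had a dose reduction at every administration.

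The stated objective is to describe adherence, so obeying the protocol should not register as falling short of it. Each arm's dexamethasone figure would also depend partly on how many of its subjects are 75 or older. Such subjects can be expected: there is no upper age limit, and the protocol cites a median age at diagnosis of 70. The planned age categories (65 to 75, over 75) do not match the dosing threshold, so an age table would not cleanly separate the effect.

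**Working it through.** **The plan's own figures.** The documents give no expected value for the cumulative-dose proportion. The nearest are the half-widths for mean relative dose intensity at n = 25, and they reproduce: 1.96 × SD/√25 = 1.96, 3.92 and 5.88 for SD 5, 10 and 15, printed as 2.0, 3.9 and 5.9. They are motivated by a carfilzomib result and are not a yardstick for the dexamethasone question.

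**1. Dexamethasone, 12 cycles on the current schedule.**
- Section 7.1.2.1: 2 × 8 × 20 + 10 × 3 × 40 = 320 + 1200 = 1520 mg.
- Section 7.4.1.2, age 75 or older: 2 × 8 × 10 + 10 × 3 × 20 = 160 + 600 = 760 mg.
- Literal rule: 760/1520 = 50.0%, and also 50% within each phase (160/320, 600/1200).
- Lower schedule counted as nominal: 760/760 = 100%.
- The SAP relative dose intensity formula, with its 20/40 mg doses on the current schedule and equal durations, also gives 50%.

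**2. Effect on an arm of 25.** With n compliant subjects aged 75 or older and everyone else at 100%, the mean is 100 − 50n/25 = 100 − 2n. The documents give no n. Assumed values of 2, 5 and 10 give 96, 90 and 80.

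**3. Which reading the text supports.**

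| Place | Points to |
|---|---|
| 10.3.2.3.1 and synopsis: only 7.1.1.2 and 7.1.2, modifications disregarded | 50% |
| 7.1.2.1 and Table 2-1: age rule labelled a dose modification | 50% |
| SAP Section 5 table: no age row | 50% |
| 7.4.1.2: lower schedule called a starting dose | 100% |
| Table 7-5: nominal 20 mg row | 100% |

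On Table 7-5: under age 75 a dosing week totals 40 mg in both phases (20 + 20, then 40). The only schedule totalling 20 mg is the one for age 75 or older, so that is the natural match for the nominal 20 mg row.

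**4. Mild-hepatic carfilzomib start, all 12 cycles, mg/m².**
- Kd: full 2 × 20 + 10 × 56 + 30 × 70 = 2700; hepatic start 2 × 15 + 10 × 42 + 30 × 53 = 2040; ratio 75.6%.
- KRd and KPd: full 2 × 20 + 10 × 27 + 30 × 56 = 1990; hepatic start 2 × 15 + 10 × 20 + 30 × 42 = 1490; ratio 74.9%.
- If 7.1.1.2.1 counts as specified therapy, the score is 100%.

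**5. Two further details in SAP Section 5.**
- For a last dexamethasone dose on Day 15 of a once-weekly cycle, the interval table gives 14 days but the weeks table credits 3 weeks. For a perfect completer, with cycle 12 treated as the last cycle, exposure is 48 weeks and protocol weeks are 4 × 11 + 3 = 47. Relative dose intensity is 47/48 = 97.9%. This matters only if dexamethasone relative dose intensity is reported: Section 5 defines it, but 9.6.9 does not list it.
- Carfilzomib mg are divided by baseline BSA, while Protocol 7.1.1.2 recalculates BSA and dose after a weight change of 20% or more. BSA varies with the square root of weight. Assume a 20% change from cycle 3 on and BSA below the cap. A compliant Kd subject then scores (600 + 2100 × √0.8)/2700 = 91.8% after a loss, or (600 + 2100 × √1.2)/2700 = 107.4% after a gain.

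**The case against.** The best defence is that the lower schedule is already nominal. Section 7.1.2.1, which the rule cites, sends these subjects to 7.4.1.2; that section speaks of a starting dose; and Table 7-5 has a nominal row that fits no other schedule. On this view the intended dose is 760 mg and nothing is wrong. This stands as a reason not to treat 50% as settled. It does not remove the problem, because the rule, the label and the SAP table point the other way.

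A second defence is that percent of full nominal dose is a legitimate descriptive measure and may be what was meant. If so, the plan should say so, and should not let compliant doses count as reductions.

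A third is that the SAP predates the current design, and the documents do not show whether the age rule existed when it was written. That is fair: the missing row is not a fault in its own time. The SAP has to be updated, and that is the place to settle the point.

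On the hepatic start, the permission to re-escalate also lies inside cited Section 7.1.1.2, so a reading that includes the lower start can include re-escalation too. A reader might infer that the plan yields scores above 100% (2550/2040 = 125% for Kd, 1910/1490 = 128% for the triplets, if re-escalated from cycle 3). That needs a denominator frozen at the starting dose, which no document specifies.

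**Conclusion.** The passages conflict and must be reconciled. Taken literally, the rule gives 50% for dexamethasone in a fully compliant subject aged 75 or older; Section 7.4.1.2 and Table 7-5 support 100%. Unless the SAP's reference to the subject's own doses overrides its fixed table, each compliant dose is also a dose reduction. The hepatic start has the smaller ambiguity of 100% against about 75%.

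Three stronger readings are not supported:
- That such a subject is half-dosed overall. The age rule concerns dexamethasone only; carfilzomib, lenalidomide and pomalidomide are unaffected, and mg and mg/m² cannot be summed.
- That a planned inference is biased. The endpoint is descriptive and reported arm by arm, so no test, error rate or sample size changes. The size in any arm depends on an unstated number of subjects, at 2 points each.
- That the 50% carries over to earlier Kd subjects on six twice-weekly and six once-weekly cycles. Halving throughout would give 840/1680, but 7.4.1.2 is written for cycles 1-2 and 3-12 only, so this would be an extrapolation.

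It is worth fixing before database lock, when Protocol 10.3 requires a final SAP, so that the denominator is not chosen after the data are seen.

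**What to change.** In the SAP update for the three arms and the schedule of two twice-weekly and ten once-weekly cycles:
- Report the dose proportion separately for each drug.
- Define intended dose and dose reduction against the starting schedule the protocol assigns to the subject at baseline: arm, schedule version, age 75 or older, baseline hepatic status.
- Keep percent of full nominal dose as a supplementary line. Report hepatic-start subjects who are re-escalated on that line (94.4% for Kd = 2550/2700 and 96.0% for the triplets = 1910/1990, if re-escalated from cycle 3). Do not switch their denominator after baseline: re-escalation is discretionary, and intended dose should not depend on a later decision.
- Make the dexamethasone Day 15 interval and weeks credit agree for once-weekly cycles.
- Divide each carfilzomib dose by the BSA used for that dose, capped at 2.2 m².

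Carry the matching sentence into Protocol 10.3.2.3.1 and the synopsis at the next amendment; a separate amendment is not needed for this alone. The cost is a few definitions and table entries in a document that must be revised anyway, using age, hepatic status, weight and dose data already collected. Only the analysis definitions change; no dose is prescribed.
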